6.1 Screened Population

Screened Population will consist of all participants with IBS-C who undergo the Screening Visit (Visit 1) and receive a participant identification (PID) number.

6.2 Randomized Population

Randomized Population will consist of all participants in the Screened Population who are randomized to a study intervention group.

6.3 Modified Intent-to-Treat Population

The Modified Intent-to-Treat (mITT) Population will consist of all participants in the Randomized Population who receive at least 1 dose of double-blind study intervention. Participants will be summarized according to the randomized study intervention for all efficacy analysis variables/endpoints.

Significant non-compliance was identified at an investigational site (Site ID 10049). As a result of this finding, efficacy data for the participants randomized at this investigational site will be excluded from the statistical analyses. Safety data for these participants will be included in the statistical analyses. There were 3 participants that were randomized at this site, who will be excluded from mITT population.

An issue was discovered in July 2021 during the implementation of adding IBS-C participants in this study by the eDiary vendor, where the inclusion criterion (#2.012) related to abdominal pain was not displayed in the eligibility report. Because of this, 8 IBS-C participants (including the 3 participants at the above site 10049) were incorrectly randomized without meeting the abdominal pain criterion. As a result of this finding, these participants will be excluded from mITT population and efficacy data for these participants will be excluded from the statistical analyses. Safety data for these participants will be included in the statistical analyses.

6.4 Safety Population

The Safety Population will consist of all participants in the Randomized Population who receive at least 1 dose of double-blind study intervention.

Participants will be summarized according to the study intervention they actually received for all safety analysis variables/endpoints. If a participant received study intervention other than

randomized study intervention, actual study intervention received will be determined based on the study intervention received for the majority of the double-blind Study Intervention Period. If there is a tie, the higher dose will be considered the actual study intervention for that participant. This is also relevant for subjects who require dose de-escalation, which is allowed once per participant to ensure safety and tolerability for study subjects. The actual study intervention will be listed for the participants in the listing related to study intervention dosing information.

7 Participant Disposition

The number and percentage of participants in 3 study populations (Randomized, mITT, and Safety) will be summarized overall, by study intervention group, country, and study center; the number of participants screened will be summarized overall, only by country, and study center.

Screen-failure participants (ie, participants who are screened but do not enter into the Preintervention Period), participants ineligible for randomization (ie, participants who enter into the Preintervention Period but are not randomized at Visit 3, also labeled as preintervention failures), and the associated reasons for failure as recorded in the electronic case report forms (eCRF) will be tabulated overall for all screened participants.

The number and percentage of participants who complete the study, complete the double-blind Study Intervention Period, complete the Postintervention Period, prematurely discontinue the study, prematurely discontinue the double-blind Study Intervention Period, and prematurely discontinue the Postintervention Period will be presented for each study intervention group and pooled across study intervention groups for the Randomized Population. The reasons for premature discontinuation from the double-blind Study Intervention Period and the Postintervention Period as recorded in the eCRF will be summarized (number and percentage) by study intervention group for the Randomized Population. All participants who prematurely discontinue during the Study Intervention Period or Postintervention period will be listed by discontinuation reason for the Randomized Population.

Please note that a participant is considered to have completed the study if he/she has completed 12 weeks of double-blind study intervention, End-of-Treatment visit, and the EOS visit. Participants who rollover to the long-term safety study, LIN-MD-66, before the EOS Visit will be considered to have completed the study if he/she has completed 12 weeks of study intervention and the End-of-Treatment Visit.

8 Demographics and Other Baseline Characteristics

Demographic parameters (age; age group [7-11 and 12-17 years (inclusive)]; race; ethnicity; sex) and baseline characteristics (weight; height; and body mass index, calculated as weight [kg]/(height [m])²) will be summarized descriptively by study intervention group for the mITT, and Safety Populations. The above demographics parameters will also be summarized by age group (7-11 and 12-17 years (inclusive)) within the Safety Population.

Other baseline characteristics (including efficacy parameters related to the bowel habits and symptoms as discussed in Section 10) will be summarized descriptively by study intervention group for the mITT Population.

Continuous variables will be summarized by number of participants, mean, standard deviation (SD), median, minimum, and maximum values. Categorical variables will be summarized by number and percentage of participants.

Abnormalities in participants' medical and surgical histories will be coded using the Medical Dictionary for Regulatory Activities, version 23.0 or newer. The number and percentage of participants with abnormalities in medical and surgical histories in each system organ class and preferred term will be summarized by study intervention group for the Safety Population.

Prior medication is defined as any medication taken before the date of the first dose of study intervention. *Concomitant medication* is defined as any medication taken on or after the date of the first dose of study intervention. Any prior medications stopped more than 30 days before the date of the first dose of study intervention and any concomitant medications started after the date of the last dose of study intervention will not be presented in the summary tables but will be included in the participant data listings.

Both prior and concomitant medications will be coded by drug name and therapeutic class. The use of prior and concomitant medications will be summarized by the number and percentage of participants in each study intervention group for the Safety Population. If a participant took a specific medication multiple times or took multiple medications within a specific therapeutic class, that participant would be counted only once for the coded drug name or therapeutic class.

The World Health Organization (WHO) Drug Dictionary, version Global B3 March 2020 or newer, will be used to classify prior and concomitant medications by therapeutic class and drug name.

Unique participants reporting significant protocol deviations will be summarized in total and by study intervention group for the Randomized Population.

9 Extent of Exposure and Study Intervention Compliance

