### 6.6. Dose Modification

For both FC and IBS-C participants, the investigator may allow a participant to stop taking study intervention for up to 3 days because of an intolerable AE. If the investigator believes that the participant is unable to resume dosing after 3 days or requires a suspension of dosing on more than 1 occasion, the investigator is required to contact the study physician to discuss the participant's continued participation in the study.

For IBS-C participants experiencing an intolerable AE that may be related to the use of linaclotide,

- those randomized to the 145 µg dose can be dose reduced in a double-blinded fashion to 72 µg linaclotide, and
- those randomized to the 290 µg dose can be dose reduced in a double-blinded fashion to 145 µg linaclotide during the course of the study at the investigator's discretion.

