9.1 Extent of Exposure

Exposure to the study intervention for the Safety Population during the double-blind Study Intervention Period will be summarized for study intervention duration, calculated as the number of days from the date of the first dose of study intervention to the date of the last dose of study intervention, inclusive. Descriptive statistics (number of participants, mean, SD, median, minimum, and maximum) will be presented by study intervention group.

Patient-years, defined as exposure to the study intervention in years, will be summarized by study intervention for the Safety Population.

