An SBM is a BM that occurs in the absence of laxative, suppository, or enema use on the calendar day of the BM or the calendar day before the BM. A complete spontaneous bowel movement (CSBM) is an SBM that is associated with a sense of complete evacuation.

The baseline SBM and CSBM weekly rates, stool consistency, straining, and abdominal symptoms (abdominal pain and bloating) will be derived as discussed in Section 16.3.5 from 14 days prior to randomization and up to randomization (as appropriate). A participant's baseline stool consistency and straining cannot be assessed if the participant does not have at least 1 SBM during the Preintervention Period. For participants who report no SBMs during a study period, the stool consistency and straining assessments will be considered missing for that study period in the analyses. Participants with missing baseline stool consistency and straining will be excluded from the respective stool consistency and straining analyses that involve change from baseline.

Baseline values for the participant-completed global change and severity items, and observer completed global change and severity items, will be based on the last non-missing assessment on or before the date of first dose of study intervention.

An observed cases (OC) approach to missing postbaseline data will be applied. Efficacy responses following onset of dose de-escalation will not be included for primary analyses. Supplemental summaries will be provided for primary and secondary endpoints by study intervention dose sequence incorporating the responses following the onset of dose de-escalation. No statistical testing will be performed to compare linaclotide doses. No multiplicity adjustment will be applied in this study for IBS-C participants.

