10.2.2 Supplemental Analysis

Weekly responder rates (counts and percentages) will be provided separately for abdominal pain weekly responders and SBM+2 weekly responders by study intervention group. By-week summary (mean, median, SD, standard error of mean, minimum, and maximum) will be provided for change from baseline in SBM frequency rate, abdominal pain, and stool consistency separately.

The descriptive statistics (mean, median, SD, standard error of mean, minimum, and maximum for continuous endpoints and counts and percentages for responder endpoints) will also be provided by study intervention sequence incorporating efficacy responses following onset of dose-de-escalation for secondary efficacy endpoints.

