11.1 Adverse Events

Adverse events will be coded by system organ class and preferred term using the *Medical Dictionary for Regulatory Activities*, version 23.0 or newer.

An AE will be considered a treatment-emergent adverse event (TEAE) if

- The AE began on or after the date of the first dose of study intervention; or
- The AE was present before the date of the first dose of study intervention, but increased in severity or became serious on or after the date of the first dose of study intervention

An AE that occurs more than 30 days after the last dose of study intervention will not be counted as a TEAE.

An AE will be considered a treatment-emergent serious adverse event (TESAE) if it is a TEAE that additionally meets any SAE criterion.

The number and percentage of participants reporting TEAEs in each study intervention group will be tabulated by descending percentage in any group, by system organ class and preferred term, and further categorized by severity and causal relationship to the study intervention. If more than 1 AE is coded to the same preferred term for the same participant, the participant will be counted only once for that preferred term using the greatest severity and strictest causality for the summarization by severity and causal relationship. The above summaries of TEAEs, further categorized by severity and causal relationship will also be provided within each age group. If there are 5 or less participants with severe or related TEAEs in any study intervention group, the

corresponding age group summaries for TEAEs by severity or causal relationship will not be provided.

The incidence of common ($\geq 5\%$ of participants in any study intervention group) TEAEs will be summarized by system organ class, preferred term, and study intervention group.

Summary tables will be provided for participants with TESAEs, AEs of special interest, and participants with AEs leading to discontinuation.

For all screened participants, separate listings will be presented for participants who died, participants with SAEs, participants with AEs leading to premature discontinuation, and participants with AEs of special interest (AESI). AEs during the Postintervention Period will also be included in the listings. A listing of all AEs will also be presented.

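### The IBS-C safety tables move participants reduced early from 290 to 145 µg into the 145 µg group, along with the adverse event that caused the reduction, and give no place to a majority dose of 72 µg

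*SAP*

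**What the plan says.** **Grouping.** IBS-C SAP 6.4 presents all safety variables by the intervention actually received, as Protocol 9.2.4 requires. Where this differs from the randomized dose, "actual study intervention received will be determined based on the study intervention received for the majority of the double-blind Study Intervention Period", and a tie goes to the higher dose. The rule is not confined to dispensing errors: "This is also relevant for subjects who require dose de-escalation, which is allowed once per participant".

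**Trigger for reduction.** Protocol 6.6 opens the option with "For IBS-C participants experiencing an intolerable AE that may be related to the use of linaclotide". It then allows one step down, from 290 to 145 µg or from 145 to 72 µg.

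**Tables.** SAP 11.1 states: "The number and percentage of participants reporting TEAEs in each study intervention group will be tabulated by descending percentage in any group". It adds: "Summary tables will be provided for participants with TESAEs, AEs of special interest, and participants with AEs leading to discontinuation". Neither sentence refers to the dose being taken when the event began. On exposure, SAP 9.1 says: "Patient-years, defined as exposure to the study intervention in years, will be summarized by study intervention for the Safety Population".

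**Efficacy is treated differently.** The opening of SAP section 10 says: "Supplemental summaries will be provided for primary and secondary endpoints by study intervention dose sequence". SAP 10.2.2 repeats the commitment for secondary endpoints: "by study intervention sequence incorporating efficacy responses following onset of dose-de-escalation for secondary efficacy endpoints". Section 11 has no counterpart for safety.

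**Columns.** Protocol 9.2.5.2 plans IBS-C safety summaries for two linaclotide dose groups. The IBS-C SAP text does not mention 72 µg.

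**The concern.** The regrouping is not independent of the outcome being tabulated. A participant changes column because of an adverse event thought possibly due to the drug, and the event changes column too. For events that these participants had, the 290 µg rate goes down and the 145 µg rate goes up. For events that they did not have, only the denominators move, giving a small shift the other way.

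Protocol 9.2.3 says the IBS-C part is sized to inform prescribers about safe and efficacious use of the doses, and the by-group TEAE tables carry the safety side of that. The two sides would also describe different people. Under SAP 6.3 and 10.1.3 an early reducer stays in the 290 µg efficacy column and is a non-responder for the weeks after the reduction, while the event that caused the reduction is counted under 145 µg.

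Separately, whoever programs the tables must decide without guidance whether a participant mostly on 72 µg forms a third column, joins 145 µg or is left out.

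**Working it through.** The plan gives no figure to reproduce, so the rule was applied by counting days and then illustrated on assumed counts.

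**1. Cut-off.** Inputs: 84 treatment days (SAP Table 4-1 footnote on the Week 12 visit), no missed doses, and the majority and tie rules of SAP 6.4. If the first 145 µg dose is on day *d*, there are *d* − 1 days on 290 µg and 84 − (*d* − 1) days on 145 µg.
- *d* = 42: 41 days versus 43 days, so the participant is tabulated under 145 µg.
- *d* = 43: 42 versus 42, a tie, so the participant stays under 290 µg.

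SAP 6.4 does not say whether the majority is of the planned 12 weeks or of the participant's own treated period. If it is the latter, the last 290 µg day that still moves a participant is Day 6, 13 or 27 for treatment lasting 14, 28 or 56 days.

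**2. Effect of one mover.** Assume 50 per arm, with *a* participants having the event in the 290 µg arm and *b* in the 145 µg arm.
- Mover had the event: (*a* − 1)/49 versus (*b* + 1)/51.
- Mover did not have it: *a*/49 versus *b*/51.

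| Assumed rates, 290 vs 145 µg | Mover had the event | Mover did not |
|---|---|---|
| 10/50 vs 5/50 (20% vs 10%) | 9/49 = 18.4% vs 6/51 = 11.8% | 10/49 = 20.4% vs 5/51 = 9.8% |
| 10/50 vs 10/50 (20% vs 20%) | 9/49 = 18.4% vs 11/51 = 21.6% | 10/49 = 20.4% vs 10/51 = 19.6% |
| 7/50 vs 6/50 (14% vs 12%) | 6/49 = 12.2% vs 7/51 = 13.7% | 7/49 = 14.3% vs 6/51 = 11.8% |

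The third row is close to the adult diarrhea rates in study MCP-103-303 (13.8% at 266 µg, 12.4% at 133 µg; Protocol Table 10-3).

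**3. More movers, all with the event, starting from 20% versus 10%.** Two give 8/48 = 16.7% versus 7/52 = 13.5%. Three give 7/47 = 14.9% versus 8/53 = 15.1%. Five give 5/45 = 11.1% versus 10/55 = 18.2%.

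**4. Exposure.** With 50 completers and one mover who took 41 days at 290 µg, the true 290 µg exposure is 49 × 84 + 41 = 4157 days. The table shows 49 × 84 = 4116. The missing 41 days (41/4157 = 1.0%) are shown as 145 µg exposure.

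**5. 72 µg.** Take 5/50 = 10.0% on 145 µg, with one of the five reduced early to 72 µg. The 145 µg column reads 5/50 = 10.0% if that participant is kept there, or 4/49 = 8.2% if not.

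**6. How many movers.** The documents give no de-escalation rate. The nearest figure is from LIN-MD-63: 29 + 21 + 24 + 8 = 82 linaclotide participants, of whom 1 discontinued for an adverse event over 4 weeks (Protocol 2.2.2). Discontinuation is not dose reduction, and only 8 of the 82 took 290 µg.

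**The case against.** The rule is pre-specified and disclosed, follows the as-treated principle of Protocol 9.2.4, and resolves ties towards the higher dose. Listings of dosing and adverse events allow individual cases to be traced. Table specifications are in a separate document, so a further display cannot be excluded. All of this is true, but listings are not incidence tables, and nothing in the SAP text corrects the TEAE tables.

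The strongest point concerns serious events. Protocol 7.1.1 requires discontinuation for an SAE at least possibly related to study intervention, and for an intervention-related AESI. Participants with those events should leave the study rather than step down, and an event that led to reduction has not, at that time, led to discontinuation. This stands as a limit on size: most misplaced events will be non-serious TEAEs. It does not exempt the other tables. Unrelated serious events before the reduction move too, as does a triggering event that persists and later ends treatment.

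It can also be said that SAP 9.1 is worded loosely on exposure, using both study intervention group and study intervention. Grouping by SAP 6.4 is the natural reading, because it governs all safety variables.

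A table by dose at onset has its own weakness: one participant can appear in two columns with unequal time at risk. That is why matching exposure is needed. Dose-sequence groups may also be very small.

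Finally, no dose comparison is tested, and the reversal in step 3 needs three or more movers with the same event, which no document supports. This bears on priority, not on whether the attribution is right.

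**Conclusion.** The concern holds on the SAP text. Followed as written, the rule attributes an event that began on 290 µg to 145 µg for any completer reduced early enough, and no planned summary undoes this. The Day 42 cut-off assumes 84 days of treatment without missed doses.

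The size is unknown and may be small. With 50 per arm, one mover who had the event shifts each rate by about 2 percentage points, and several could erase or reverse a displayed difference. All event rates used here are assumptions. No true dose difference is presumed: Protocol 2.2.1 reports that adult TEAE incidence was not related to dose, and adult study LIN-MD-01 had more diarrhea at 133 µg (19.7%) than at 266 µg (14.6%). Even equal true rates would be displayed as unequal.

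IBS-C safety is descriptive, so no test or efficacy conclusion changes. The 72 µg question alone would only be a missing detail. The attribution rule should be corrected.

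**What to change.** Keep the as-treated Safety Population if preferred, and make these changes:

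- **SAP 11.1:** add a TEAE summary, covering TESAEs, AESIs and events leading to discontinuation, by the dose being taken at onset, or by dose sequence as already planned for efficacy.
- **SAP 9.1:** give exposure by dose actually taken, so that the new table has matching time at risk.
- **SAP 6.4:** state where participants whose majority dose is 72 µg are displayed, and whether the majority is of the planned 12 weeks or of the participant's own treated period.
- **SAP 17:** record the change.

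A safety table by randomized dose could be added as support.

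The cost is one or two extra tables and a few sentences. The onset of de-escalation is already needed for the efficacy rules in SAP 10.1.3, so no new data or participants are required. The change concerns display only and leaves the dosing rules as they are.

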#### **9.2.5.2. Safety Analyses**

The safety analysis will be performed separately using the safety population for IBS-C participants. The safety parameters will include AEs, clinical laboratory parameters, vital sign measurements, height, weight, and ECG parameters. For each safety parameter, the last non-missing assessment made before the first dose of double-blind study intervention will be used as

the baseline for all analyses of that safety parameter. The safety analyses in IBS-C participants will be conducted similarly as discussed in Section 9.1.5.2 for FC participants with the exception that the summary will be provided for each of the two linaclotide dose groups.

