10.1.3 Estimand Framework

Population

The target population is participants with IBS-C, ages 7-17 years old, satisfying the inclusion and exclusion criteria as specified in Sections 5.1 and 5.2 of the protocol (Version June-2020), respectively.

The analysis population is mITT as discussed in Section 6.3.

Variable

The variable is the primary efficacy endpoint defined in Section 10.1, which is 6/12 weeks APS (abdominal pain and SBM) + 2 responder as derived from twice daily responses in eDiary (morning and evening). SBM is derived based on responses for BM and rescue medication in the eDiary twice daily (morning and evening). Abdominal pain score is also derived based on responses in the eDiary twice daily for abdominal pain.

Accounting for Intercurrent Events in the Primary Efficacy Analyses

The following intercurrent events are considered for the primary efficacy analyses. All the intercurrent events are handled based on the composite strategy.

- The BMs for the participants who took a laxative, enema, or suppository on the calendar day of the BM or the calendar day before the BM will not be considered as SBMs for the analysis.
- Participants who discontinue prematurely during but prior to the completion of the double-blind Study Intervention Period will have their eDiary data included up to the morning diary following the last dose date for primary endpoint. The early discontinued participants will be considered non-responders for the following weeks for primary endpoint.
- eDiary responses following the onset of dose de-escalation will not be included. The participants with dose de-escalation will be considered non-responders for the subsequent study intervention weeks (after the onset of dose de-escalation) for the primary endpoint based on the randomized study intervention group.
- A participant has to have at least 4 completed diary days per study intervention week to be considered a responder for that week and otherwise, the participant will be considered non-responder for that week. A completed diary day is a day in which both morning and evening eDiary entries are filled out by a study participant.

Population-level Summary

The population-level summary for the primary endpoint is the proportion of participants satisfying the APS + 2 responder criteria for at least 6 out of 12 weeks during the study intervention period for each linaclotide dose.

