10.4 Subgroup Analysis for Efficacy endpoints

Primary and secondary efficacy endpoints will be summarized in a similar way as discussed for main analysis approach for the following subgroups (within each subgroup category) based on the mITT Population. Subgroups will be interpreted with caution due to possible limited sample size within each subgroup category.

- Age group (7-11 years group, 12-17 years group)
- Race (white, non-white)
- Gender (male, female)

11 Safety Analyses

The safety analysis will be performed using the Safety Population. The safety parameters will include adverse events (AEs) and clinical laboratory parameters, vital sign (including postural), electrocardiographic (ECG) parameters, height, and weight. For each safety parameter of the clinical laboratory, vital signs, height, weight, and ECG parameters, the last non-missing safety assessment before the first dose of study intervention will be used as the baseline for all analyses of that safety parameter. Continuous variables will be summarized by number of participants and mean, SD, median, minimum, and maximum values. Categorical variables will be summarized by number and percentage of participants. The safety summaries will be provided by study intervention group.

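### IBS-C safety tables file a de-escalated child under the dose taken longest, so TEAEs that begin on 290 µg before an early step-down are counted under 145 µg

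*SAP*

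**What the plan says.** - **Grouping rule.** IBS-C SAP 6.4 summarizes safety by intervention received. For a child who took something other than the randomized dose, "actual study intervention received will be determined based on the study intervention received for the majority of the double-blind Study Intervention Period". On ties: "If there is a tie, the higher dose will be considered the actual study intervention for that participant".
- **Scope.** The same section adds: "This is also relevant for subjects who require dose de-escalation, which is allowed once per participant to ensure safety and tolerability for study subjects". FC SAP 6.4 has the same majority and tie rules without this sentence.
- **Trigger.** Protocol 6.6 introduces step-down with "For IBS-C participants experiencing an intolerable AE that may be related to the use of linaclotide". The permitted steps are 290 to 145 µg and 145 to 72 µg.
- **Columns.** Protocol 9.2.5.2 carries over the FC safety analyses "with the exception that the summary will be provided for each of the two linaclotide dose groups". IBS-C SAP 11 says: "The safety summaries will be provided by study intervention group".
- **Dose-sequence output.** IBS-C SAP 10 and 10.2.2 plan summaries by dose sequence for the primary and secondary efficacy endpoints only. For safety, the text offers a dosing listing that shows the actual intervention. It specifies no TEAE table by dose at onset, by randomized dose or by dose sequence.

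**The concern.** A majority-dose rule suits a dispensing error, where the wrong bottle has nothing to do with how the child fares. Here it is extended to a planned step-down that happens because of a safety event, so the event helps to decide the column in which it is counted. A child who cannot tolerate 290 µg and steps down early leaves the 290 µg numerator and denominator, and takes the event into the 145 µg column.

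The IBS-C part has no placebo arm, so 290 against 145 µg is its only internal safety contrast. Its stated purpose is to inform prescribers about safe and effective use of these doses (protocol 9.2.3, SAP 14). Protocol Table 2-2 shows that children aged 7 to 11 received no 290 µg in LIN-MD-63, so for them this study supplies the 290 µg safety data that the Phase 2 study could not.

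**Working it through.** **1. Cut-off day.** The intervention period is 12 × 7 = 84 days, which agrees with the SAP's own figure (Table 4-1 footnotes). Let *h* be the days on the starting dose and *T* the days treated. The child goes to the lower dose if *T* − *h* > *h*; otherwise the child stays with the higher dose, because ties go up.

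- *T* = 84: 41 days on 290 µg and 43 on 145 µg gives 145 µg; 42 and 42 is a tie and gives 290 µg. The last 290 µg day that still moves the child is day 41.
- *T* = 87 (Visit 7 window of +3 days): day 43.
- If the majority is taken over days actually treated: day 34 for *T* = 70, day 27 for 56, day 20 for 42 and day 13 for 28. The SAP does not say whether planned or treated days are meant.

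The same arithmetic makes 72 µg the actual dose of a 145 µg child who steps down by day 41.

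**2. Effect on a TEAE percentage.** The documents give no step-down rate, so these are assumed cases. Take 50 per arm (the planned minimum). Let *a* and *b* be the children whose TEAE began on the randomized dose of 290 and 145 µg, and *m* the number of those *a* children who step down early. The tables then show:

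- 290 µg: (*a* − *m*)/(50 − *m*)
- 145 µg: (*b* + *m*)/(50 + *m*)

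| True counts | *m* | Shown, 290 µg | Shown, 145 µg |
|---|---|---|---|
| 5 and 5 | 1 | 4/49 = 8.2% | 6/51 = 11.8% |
| 8 and 8 | 1 | 7/49 = 14.3% | 9/51 = 17.6% |
| 8 and 8 | 2 | 6/48 = 12.5% | 10/52 = 19.2% |
| 10 and 10 | 1 | 9/49 = 18.4% | 11/51 = 21.6% |
| 10 and 7 | 2 | 8/48 = 16.7% | 9/52 = 17.3% |

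With equal true counts of 5 to 10, one child creates a false gap of 3.2 to 3.6 points. In the last row the true order, 20% against 14%, is reversed. Counts of 5 to 10 are 10% to 20%; for comparison, diarrhea on linaclotide in the adult placebo-controlled IBS-C trials of protocol Table 10-3 ranges from 4.6% to 19.7%.

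**3. Age groups.** SAP 11.1 also plans TEAE summaries by age group. With at least 40% in each stratum and an even split between arms, a stratum has 20 to 30 children per arm. At a true 20% in both arms, one early step-down gives 3/19 = 15.8% against 5/21 = 23.8% (8.0 points) with 20 per arm, or 5/29 = 17.2% against 7/31 = 22.6% (5.3 points) with 30.

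**4. Offset.** If one affected 145 µg child also moves to 72 µg and out of the two columns, the 10 and 7 case becomes 8/48 = 16.7% against 8/51 = 15.7%. The order returns, but only because a child has left both columns.

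**5. By dose at onset.** In the 10 and 7 case with *m* = 2, the denominators are children ever exposed to each dose. If neither stepped-down child has a new event on 145 µg, the result is 10/50 = 20.0% against 7/52 = 13.5%, so each event stays with the dose on which it began.

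**The case against.** - **Protocol 9.2.4 already requires safety by intervention received.** This stands. IBS-C SAP 6.4 makes that rule operational. Efficacy counts a step-down as non-response "for the primary endpoint based on the randomized study intervention group", and a reader might infer that the two are inconsistent. They are the ordinary as-treated and as-randomized split, not an error.
- **Not every safety result is misplaced.** A reader might infer that all safety output is affected. Scheduled post-baseline laboratory tests and ECGs take place only at end of treatment, when a child who stepped down by day 41 of 84 has had at least 43 days on the lower dose. The majority rule files those results under the dose being taken. Vital signs at Weeks 2 and 4 may precede the step-down, but the clear fault is with TEAEs that start before it.
- **Randomized dose as the main grouping** is a tempting cure. It would file those end-of-treatment results, and TEAEs that begin after the step-down, under a dose the child had left. That is the opposite misattribution.
- **The gravest events should not move.** Protocol 7.1.1 requires discontinuation for possibly related SAEs and intervention-related AESIs, so mainly non-serious intolerable AEs are at issue. SAP 7 tabulates discontinuation reasons for the Randomized Population, but a child who steps down and completes does not appear there.
- **Step-downs may be rare.** The Phase 2 text reports two diarrhea discontinuations on linaclotide among 214 children: 2/214 × 50 ≈ 0.5 per arm. Discontinuation is only a proxy for step-down, those studies lasted 4 weeks, and only 8 children took 290 µg.
- **The 72 µg column.** A reader might infer that the tables certainly lack one, or that a small third column would trigger the suppression rule that begins "If there are 5 or less participants with severe or related TEAEs in any study intervention group". Both depend on table specifications held in a separate document. The text shows only that 72 µg lies outside the two groups of protocol 9.2.5.2.

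**Conclusion.** The point holds for TEAEs that start on the randomized dose before an early step-down. The SAP tabulates them under the lower dose, and for 290-to-145 µg children the direction is known: 290 µg looks better and 145 µg worse. No safety table described in the SAP corrects this. A 145-to-72 µg child has no defined place in the two-group tables.

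The size cannot be derived from the documents. It is zero if no child steps down early; the illustrated 3.2 to 3.6 points per child rest on 50 per arm and assumed equal counts of 5 to 10. Day 41 is exact only for 84 treated days. No hypothesis test is affected, because the IBS-C doses are not formally compared. The change should be made: the bias is directional, it affects the only internal dose-safety contrast, and it costs little to remove.

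**What to change.** Before unblinding, amend IBS-C SAP 6.4 and 11.1 for protocol-permitted de-escalation:

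1. Add a TEAE summary by dose at AE onset (290, 145 and 72 µg), with patient-days at each dose.
2. Report the number de-escalated, and the TEAEs leading to de-escalation, by randomized dose.
3. State that 145-to-72 µg children appear in the 145 µg column of the two-group tables.
4. State whether the majority is of planned or treated days.

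The majority rule may stay for dispensing errors and for the main as-treated tables. The de-escalation date is already needed for the primary estimand (SAP 10.1.3), and AE start dates for the TEAE definition. The cost is one or two extra tables, in which a child may be counted under more than one dose in the onset-dose summary.
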